## SCHEDULE OF EVENTS

	Screening 	Part 1							Part 2
Visit Number	1	2	3 	4	5	6	7 	8	9
Visit Type	Clinic	Clinic	Phone	Clinic	Clinic	Clinic	Phone	Clinic	Clinic
Day	-45 to -7	1	2	8+1	15±2	29±3	43±3	57±4	84±4
Informed Consent/Assent	X	X							
Demographics	X								
I/E Criteria	X	X 							
Medical/Ichthyosis History 	X	X							
Brief Physical Examination	X					X		X	X
Vital Signs 	X					X		X	X
UPT for WOCBP	X	X				X		X	X
Fitzpatrick Skin Type	X								
Clinical Laboratory Tests	X					X		X	X
Genetic Testing	X 								
Selection of Treatment Areas 		X							
IGA Scores	X	X		X	X	X		X	X
CI Sign / Symptoms		X		X	X	X		X	X

 Screening window at -7 days allows clinical lab tests to be finalized and test article to be shipped prior to Visit 2/Baseline.

 Unscheduled Visits may be performed in the clinic at the investigator's discretion, if there is a concern regarding tolerability or other AE.

 Subjects who do not meet the I/E criteria at Visit 2 will be classified as screen failures.

 Any change in Medical History from Visit 1/Screening to Visit 2/Baseline is not considered an AE, but will be captured as baseline Medical History. Ichthyosis history will only be captured at Visit 1/Screening.

 Vital signs will include weight and height at Visit 1/Screening.

 For those subjects who do not have genetic test confirmation of their clinical diagnosis of X-linked or lamellar ichthyosis, blood or buccal samples will be collected.

 Each contralateral Treatment Area must be comparable in size ( $\geq 150\text{cm}^2$ ) and have the same IGA score of 3 (moderate) or 4 (severe) at Baseline and be contained within a discrete anatomic unit that shall not exceed 6% BSA. Location by body region and percent BSA of disease affected skin in each Treatment Area will be documented. Percent BSA will be estimated using the assumption that 1% BSA is equivalent to the area of the subject's hand with fingers held together. [Note: Palms and soles are not eligible; the treatment of scalp and skin folds/intertriginous regions should be avoided]. Additionally, for treatment on the arms in subjects participating in the PK portion, the antecubital fossa (e.g., approximately  $10\text{-}15\text{ cm}^2$ ) will be excluded to minimize contamination of PK blood draws.

Visit Number	Screening 	Part 1							Part 2
	1	2	3 	4	5	6	7 	8	9
Visit Type	Clinic	Clinic	Phone	Clinic	Clinic	Clinic	Phone	Clinic	Clinic
Day	-45 to -7	1	2	8+1	15±2	29±3	43±3	57±4	84±4
LSR		X  Pre&Post		X	X	X		X  Pre&Post	X
Photography		X		optional	optional	X		X	X
PK Blood Draws (optional)		X  Pre, 1, 2, 3, & 4 hr		X 	X 	X 		X 	X 
Randomization	X 	X							
Part 1: Dosing at the Clinic		X		X 	X 	X 			
Part 2 Dosing & Per Protocol Instructions								X 	
Test Articles Accountability: Dispense/Collect/Weigh –Part 1 Dosing		X		X	X	X		X	
Test Articles Accountability: Dispense/Collect/Weigh – Part 2 Dosing								X	X
Compliance / Diary Review 		X	X	X	X	X	X	X	X
Concomitant Medications and Therapies	X	X	X	X	X	X	X	X	X
Adverse Events		X	X	X	X	X	X	X	X

 LSRs will be evaluated pre- and post-test article application on Day 1 and Day 57.

 On Day 1, PK blood samples will be collected for isotretinoin and tretinoin pre-test article application (time 0) and at 1, 2, 3, and 4 hours post-application.

 On Days 8, 15, 29, 57, and 84, a PK blood sample will be collected for isotretinoin and tretinoin pre-test article application (approximately 12 hours ± 30 minutes after the last test article application on the previous day).

 Prior to Visit 2/Baseline, after laboratory results have been received and reviewed, a randomization request will be placed by the site in order for the test article to be provided to the site prior to baseline. Note: the ordered test article is specific to each subject and shall not be used for any other subject.

 If possible, the subject will apply one of the daily doses in the clinic under staff supervision to reinforce proper use.

 In Part 2, subjects will enter an active only treatment follow-up period of four weeks in which both Treatment Areas identified in Part 1 will be treated with the active test article of their assigned treatment group.

 Subject Diary will be reviewed; compliance will be discussed based on review of Subject Diary and Test Article Accountability, as applicable.

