
Study Procedures
	
The study will consist of two parts. There will be one Screening Visit, five scheduled clinic visits, and two phone calls in Part 1 and one additional clinic visit in Part 2. Subjects will have the option to participate in the PK portion of the study. Note: Subjects that elect to participate in the PK portion of the study should do so with the intent of completing all PK samplings required in the study, per protocol.
 
Visit 1: Screening (Day -45 to -7): At Visit 1, study staff will explain the study procedures and an informed consent/assent must be signed prior to the initiation of any study-related procedures. Demographics, inclusion/exclusion (I/E) criteria, medical/ichthyosis history, and prior/concomitant medications and therapies will be reviewed to determine subject eligibility. Subjects that require a "washout" period prior to enrollment into the treatment phase to meet I/E criteria requirements will be required to return to the clinic within 45 days to complete the remaining activities. Subjects who require "washout" for longer than 45 days will be re-consented. A brief physical examination including vital signs, UPT (if applicable), Fitzpatrick Skin Type assessment, and clinical laboratory testing will be performed at this visit. For those subjects who do not have confirmation of their clinical diagnosis of X-linked or lamellar ichthyosis, blood or buccal samples will be collected for genetic testing. Qualified subjects must have two comparable in size (<math>\geq 150 \text{ cm}^2</math>), contralateral Treatment Areas (per protocol) identified with equal IGA scores (i.e.,

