--	--

	
investigator. In the event that a clinic visit is not possible or not warranted in the opinion of the investigator, the change in the subject's management will be clearly documented in the source documents and case report forms (CRFs) with corresponding changes noted in the Subject Diary regarding test article usage and/or concomitant medications/therapies (e.g., moisturizer use).
 
Modifications to the dosing regimen and/or concomitant medication/therapy use may be prescribed by the investigator to manage intense LSRs and must be documented in the CRFs. Any dosing modifications will be made bilaterally (e.g., if dosing is decreased to once a day given tolerability issues, both sides will be treated once daily, even if only one side is having the tolerability issue). Frequency of dosing may be reduced to once per day (QD) or rest periods of up to several days may be allowed. Treatment per protocol should resume as soon as possible after any notable LSRs have materially subsided as determined by the investigator or designee (if possible via one of the scheduled clinic visits or via an Unscheduled Visit) such that dosing may resume. Additionally, use of provided bland emollient in the Treatment Area as an aid to managing LSRs may be prescribed with the approval of the investigator and must be documented in the CRFs. In the event that additional moisturizer use is needed (i.e., greater than QD or BID or in lieu of the test articles) in the opinion of the investigator, such therapy may be used, must be documented in the CRFs, and the investigator must notify the Medical Monitor promptly. Note: Bland emollients should not be applied within four hours of application of the test articles. No other topical therapy within the Treatment Area or in the surrounding skin within one inch of the Treatment Area is permitted.
 
Visits 3 and 7: Phone Call (Day 2 and Day 43±3): The site staff will contact the subject (or parent/guardian as applicable) by telephone to review the Subject Diary, test article compliance, changes in concomitant medications and therapies, query the subject about AEs, and confirm the next visit appointment. The site staff will remind the subject (and parent/legal guardian, if applicable) to continue to apply test article twice daily until the next clinic visit. Subjects with tolerability issues will ideally be scheduled for an in-office follow-up visit, but at the discretion of the investigator, as an Unscheduled Visit to stop/re-start/modify the dosing regimen.
 
Visits 4 and 5 (Days 8+1 and 15±2): Subjects will return to the clinic and will be queried for any changes in health status and concomitant medications and therapies. Clinical evaluations (IGA, CI Signs/Symptoms, and LSRs) for both Treatment Areas will be performed and photographs (optional) may be taken. For those subjects participating in the PK portion of the study, a PK blood sample will be collected. Note: this sample will be collected 12 hours ± 30 minutes after the dose on the previous day. Test article accountability will be documented and compliance will be reviewed (based on review of Subject Diary and weights of test articles) with the subject and

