## **6. TEST ARTICLES AND REGIMEN**

### **6.1 Description**

PAT-001 is a pale yellow, viscous ointment. Vehicle ointment is color matched to the active test article. In Part 1, each subject shall receive two test articles: a vehicle ointment and an active ointment product (either 0.1% or 0.2% PAT-001) for treatment to the left and right Treatment Areas. The test articles will be blinded using color coded labeling as detailed in [Section 6.2](#) and [Appendix 1](#) to facilitate proper use during the study period. In Part 2, each subject will receive the active ointment product assigned in Part 1 for both Treatment Areas.

Test Article Name: PAT-001 (isotretinoin) Ointment, 0.1%  
Active ingredient: isotretinoin, USP  
Other ingredients: super refined polyethylene glycol (PEG) 400, PEG 1450, PEG 3350, methylparaben, butylated hydroxytoluene, and propyl 4-hydroxybenzoate, propylparaben

Test Article Name: PAT-001 (isotretinoin) Ointment, 0.2%  
Active ingredient: isotretinoin, USP  
Other ingredients: super refined PEG 400, PEG 1450, PEG 3350, methylparaben, butylated hydroxytoluene, and propyl 4-hydroxybenzoate, propylparaben

Test Article Name: Vehicle Ointment  
Other ingredients: super refined PEG 400, PEG 1450, PEG 3350, methylparaben, butylated hydroxytoluene, and propyl 4-hydroxybenzoate, propylparaben; color additive

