- Collect urine and blood samples for clinical laboratory tests. If possible, subject will have fasted for approximately eight hours or more prior to these laboratory tests.
- Perform IGA for each Treatment Area.
- Assess CI Signs/Symptoms for each Treatment Area.
- Document LSRs for each Treatment Area.
- Take photographs.

- For those subjects participating in the PK portion of the study, collect PK blood sample PRIOR to the application of the test articles. Note: This sample will be collected 12 hours  $\pm$  30 minutes after the dose on the previous day.
- Document test article accountability; weigh the tubes and return the test articles from Part 1. Dispense the test article for Part 2 to the subject.
- Re-educate the subject (and parent/legal guardian, if applicable) with respect to dosing and related activities for Part 2.
  - Review compliance and collect/dispense Subject Diary, as applicable.
  - Supervise the application of the test article to both Treatment Areas.
- Record any AEs.
- Assess LSRs approximately 10 minutes post-application for each Treatment Area.
- Schedule Visit 9.

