### 10.4 Local Skin Reactions

At each clinic visit (except Visit 1/Screening), LSRs including burning/stinging, pain, and pruritus will be documented in each Treatment Area using a four-point ordinal scale where 0=none, 1=mild, 2=moderate, and 3=severe. These LSRs will be collected independently

of AEs. Only LSRs that require medical intervention (e.g., prescription medication) or require withholding or reduction in dosing frequency of the test articles will be documented as AEs. Any LSRs that are not listed above will be recorded as AEs.

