### 17.2 Endpoints

#### 17.2.1 Safety Endpoints

Safety endpoints will include:

- Incidence (severity and causality) of any local and systemic AEs
- Number of subjects with presence (and severity) of the following LSRs: stinging/burning, pain, and pruritus at each time point for each Treatment Area collected (summarized by Test Article).
- Changes from Screening in vital signs at Days 29, 57, and 84 (or EOT) (summarized by Treatment Group).
- Changes from Screening in clinical laboratory tests (hematology, chemistry, and urinalysis) at Days 29, 57, and 84 (or EOT) (summarized by Treatment Group).
- UPT results in all WOCBP at Screening, Baseline, Day 29, Day 57, and Day 84 (or EOT).

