#### 17.2.3 Efficacy Endpoints

Part 1 (P1) and Part 2 (P2) efficacy data will be analyzed separately. For Part 1, efficacy endpoints will be summarized by Test Article (PAT-001, 1%; PAT-001, 0.2%; and Vehicle [pooled across Treatment Groups]) and/or by Part 1 Treatment Group (Group 1: PAT-001, 0.1%/Vehicle; and Group 2: PAT-001, 0.2%/Vehicle) as described below. For Part 2, efficacy endpoints will be summarized by Part 2 Summary Group, which consists of four groups:

- Group A: PAT-001, 0.1%-P2 Active/P1 Active
- Group B: PAT-001, 0.1%-P2 Active/P1 Vehicle;
- Group C: PAT-001, 0.2%-P2 Active/P1 Active; and
- Group D: PAT-001, 0.2%-P2 Active/P1 Vehicle.

In Part 1, the following exploratory endpoints will be evaluated:

- Frequency distribution of IGA and CI Signs/Symptoms at Baseline, and Days 8,

- 15, 29, and 57 summarized by Test Article.
- Absolute change from Baseline in IGA and the CI Signs/Symptoms at Days 8, 15, 29, and 57 summarized by Test Article.
  - Within subject difference in IGA and CI Signs/Symptoms at Baseline and Days 8, 15, 29, and 57 summarized by Part 1 Treatment Group.
  - Within subject difference in change from Baseline in IGA and CI Signs/Symptoms at Baseline and Days 8, 15, 29, and 57 summarized by Part 1 Treatment Group.

In Part 2, the following exploratory endpoints will be evaluated:

- Frequency distribution of IGA and CI Signs/Symptoms at Day 84 summarized by Part 2 Summary Group (Group A-D).
- Absolute change from Baseline in IGA and CI Signs/Symptoms at Day 84 summarized by Part 2 Summary Group (Group A-D).
- Absolute change from Day 57 in IGA and CI Signs/Symptoms at Day 84 summarized by Part 2 Summary Group (Group A-D).
- Within subject difference in IGA and CI Signs/Symptoms at Day 84 summarized by Part 2 Treatment Group (0.1% and 0.2%).
- Within subject difference in absolute change from Baseline in IGA and CI Signs/Symptoms at Day 84 summarized by Part 2 Treatment Group (0.1% and 0.2%).
- Within subject difference in absolute change from Day 57 in IGA and CI Signs/Symptoms at Day 84 summarized by Part 2 Treatment Group (0.1% and 0.2%).

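### After the former vehicle area gets its first active dose at Day 57, no LSR grade is planned until Day 84, and the Part 2 LSR summaries do not separate that area from the one already on active drug

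*Combined protocol and SAP*

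**What the plan says.** Section 6.1 sets the Part 2 treatment: "In Part 2, each subject will receive the active ointment product assigned in Part 1 for both Treatment Areas". The former vehicle area therefore has its first active dose at Visit 8.

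The Schedule of Events (footnote 15) gives Day 57 the same dosing-day check as Day 1: "LSRs will be evaluated pre- and post-test article application on Day 1 and Day 57". Section 9.6 sets its timing: "Assess LSRs approximately 10 minutes post-application for each Treatment Area".

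The synopsis (Study Procedures) sets the contacts: "two phone calls in Part 1 and one additional clinic visit in Part 2". The calls fall on Day 2 and Day 43. For those calls it adds: "Subjects with tolerability issues will ideally be scheduled for an in-office follow-up visit", at the investigator's discretion.

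Section 10.4 collects burning/stinging, pain and pruritus separately from AEs. The only ones that become AEs are these: "Only LSRs that require medical intervention (e.g., prescription medication) or require withholding or reduction in dosing frequency". The synopsis version of the rule leaves out reduced dosing frequency. Both versions send any skin reaction outside the three listed symptoms to the AE data.

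Section 17.2.1 lists the safety endpoint: "Number of subjects with presence (and severity) of the following LSRs: stinging/burning, pain, and pruritus at each time point for each Treatment Area collected", summarised by Test Article. Section 17.2.3 separates the areas by Part 1 history for efficacy: "For Part 2, efficacy endpoints will be summarized by Part 2 Summary Group", that is, Groups A to D.

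**The concern.** Safety and tolerability are the primary objective, and the ointment has not been used in humans before. Section 14.1 names skin pain, application site pruritus, burning and stinging among the common reactions to other topical retinoids, so the three graded symptoms are the expected ones.

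The plan recognises Day 57 as a first exposure by repeating the pre- and post-application check, but it schedules nothing for the following weeks. A clean Day 84 grade in a former vehicle area could mean that no reaction occurred, or that one came and went.

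The summary has a related weakness. From the Day 57 post-application grade onward, both areas of a subject are on the same test article. A table by Test Article then mixes an area in its first four weeks of active treatment with one in its ninth to twelfth week. That hides any first-exposure effect the data do contain.

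**Working it through.** The plan has no power or precision figure to reproduce here. The check is a count of planned grades, followed by an illustration.

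**Intervals (Schedule of Events)**
- Part 1: first active dose Day 1; LSR grades on Days 8, 15, 29 and 57, which is 7, 14, 28 and 56 days later. The Day 2 call has no LSR entry.
- Part 2, former vehicle area: first active dose Day 57; LSR grade on Day 84. 84 − 57 = 27 days. Shortest with ±4-day windows: 80 − 61 = 19. Longest: 88 − 53 = 35.
- Grades in the first 14 days after first active dose, beyond the 10-minute check: 2 in Part 1, 0 in Part 2.

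These counts need no assumption.

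**Where an ungraded episode could be recorded**
- *Scheduled LSR grade:* none between Visits 8 and 9.
- *AE form:* AEs are collected at Visit 9, but Section 10.4 excludes a listed symptom that needed no intervention, withholding or reduction.
- *Diary (Appendix 2):* dose times and areas dosed only.
- *CRF (Sections 6.2 and 8.2):* prescribed bland emollient, dosing changes and other changes in management are recorded.
- *Unscheduled Visit:* possible, but discretionary.

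What remains is an episode of a listed symptom that triggers none of these.

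**Illustration of the chance of a grade**

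The documents give no onset or duration. Assume onset s is uniform over days 0 to 14 after first active dose, duration is d days, and a grade records only what is present at that moment. A grade on day g catches the episode if s ≤ g ≤ s + d, so it covers onsets from g − d to g. The capture fraction is the length of the union of these intervals within 0 to 14, divided by 14.

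Nominal days:
- Part 1 (g = 7, 14, 28). d = 3: onsets 4–7 and 11–14, 6/14 = 43%. d = 7: 0–7 and 7–14, 100%. Longer d: 100%.
- Part 2 (g = 27). d = 3 and d = 7: none. d = 14: 13–14, 1/14 = 7%. d = 21: 6–14, 8/14 = 57%.

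With windows in both parts:
- Part 1 (g = 7–8, 12–16, 25–31). Lowest for d = 3: second grade at 16, 4/14 = 29%. For d = 7: grades at 8 and 12, onsets 1–12, 11/14 = 79%. For d = 14: grades at 12 and 31, onsets 0–12, 12/14 = 86%. For d = 21: 100%.
- Part 2 at g = 19: 0; 2/14 = 14%; 9/14 = 64%; 100%. At g = 35: 0 throughout.

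| Duration | Part 1, nominal (range) | Part 2, nominal (range) |
|---|---|---|
| 3 days | 43% (29–43%) | 0% (0%) |
| 7 days | 100% (79–100%) | 0% (0–14%) |
| 14 days | 100% (86–100%) | 7% (0–64%) |
| 21 days | 100% (100%) | 57% (0–100%) |

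**With added grades 1, 7 and 14 days after Visit 8** (g = 1, 7, 14, 27). d = 3: onsets 0–1, 4–7 and 11–14, 7/14 = 50%. Longer d: 100%. If the two later calls may move by ±2 days, the 7-day figure can fall to 10/14 = 71% (calls at 5 and 16, onsets 0–5 and 9–14). The longest ungraded stretch falls from 27 days to 13 (Day 71 to Day 84).

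**The case against.** The strongest reply is that little is lost. Part 1 gives full early grading of about 18 active areas, 9 per concentration. Reactions that lead to treatment, emollient, a dose change or a visit are recorded. Unlisted reactions such as redness or peeling go to the AE data. Appendix A 3.5 tells subjects to contact the site about irritation or rash. What remains is the mildest kind of episode, in a follow-up period without concurrent vehicle, where pruritus may be the disease itself. All of this stands, and it limits the point to a small one. It does not supply a grade for the episodes that remain.

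A reader might infer that early reactions in general go unrecorded in Part 2. The documents do not support that: the gap covers three symptoms and only episodes without action. Nor is a missing counterpart to the Day 2 call a reason for lost LSR data. That call collects no LSR grade, and a symptom mentioned on it still falls under the Section 10.4 rule.

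A reader might also count 18 areas per concentration instead of 9 and lower the zero-event 95% upper limit from 1 − 0.05^(1/9) = 28.3% to 1 − 0.05^(1/18) = 15.3%. That is wrong here. The endpoint counts subjects, and Part 2 adds a second area in the same 9 or so subjects, already exposed to that strength for eight weeks. Discontinued subjects are not replaced, so those who remain may be the more tolerant ones. With strong within-subject correlation the gain in precision is close to nil.

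On the summary, Section 4 allows safety and tolerability measures to be evaluated by Summary Group where applicable and points to Section 17. Section 17 applies those groups to efficacy only.

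**Conclusion.** The point holds as a minor, inexpensive improvement. The former vehicle area has no planned LSR grade between 10 minutes and 27 days (19 to 35) after its first active dose, against grades at 7, 14 and 28 days in Part 1. Listed symptoms that settle in that interval without any recorded action have no planned LSR or AE record. As written, the Part 2 LSR summary also merges first-exposed with long-exposed areas.

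The counts and the AE rule come straight from the documents. The capture percentages rest on assumed onset, assumed duration and point-in-time grading; Section 10.4 states no recall period, so they are illustrative only. A reader might infer that tolerability of either concentration cannot be judged, or that subjects are left unprotected. Neither follows: the Part 1 data are intact, and the routes for managing reactions apply in Part 2 as well. What is missing is early tolerability information from a second area in the same subjects.

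**What to change.** 1. In Section 17.3.1, tabulate the Day 57 post-application and Part 2 LSRs by Part 2 Summary Group A to D, as already planned for efficacy. This uses data already collected and costs nothing beyond the table.

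2. Add short calls the day after Visit 8 and about 7 and 14 days after it, counted from the actual visit date. Ask about AEs and record burning/stinging, pain and pruritus (0 to 3) for the right and left areas. Label these grades as phone-reported and list them apart from clinic grades. Leave the Section 10.4 AE rule and Section 6.2 dose management as they are.

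Cost: at most 3 × 18 = 54 calls by existing staff, with no added clinic visit, blood draw or test article. Phone grading is a different mode from the Part 1 clinic grading, so the two should not be compared as if they were the same. The calls need a protocol amendment with IRB approval, covering the synopsis, the Schedule of Events, Sections 9.6, 10.4 and 17.3.1, and the CRF.
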